1 PROTOCOL SUMMARY

1.1 SYNOPSIS

Title:	Development and Evaluation of Novel Dynamic Bar for Foot Abduction
	Brace for Clubfoot Treatment
Study Description:	This is an assessor-blinded randomized feasibility trial assessing the feasibility of conducting a large-scale clinical trial to evaluate the effectiveness of a new dynamic bar for foot abduction bracing for clubfoot treatment. Feasibility will be determined by the ability to recruit patients within the goal study period and to retain participants. Eligible patients must have a well-corrected idiopathic clubfoot (Pirani Score ≤ 0.5) and be in the minimum 12 hours per day bracing stage of the Ponseti clubfoot treatment protocol. The overall study period will be 90 days in length. For the first 30 days, the experimental cohort will wear the new Dynamic Bar (DB) with standard ankle-foot orthoses (boots) and the control cohort will continue wearing their Standard Bar (SB). After this 30-day period, the experimental cohort will return to wearing their SB.
	All patients will be evaluated on Day 0, Day 7, Day 30, and Day 90 of the study period to monitor for recurrence of the clubfoot deformity, complications of brace wearing, to submit brace wear logs, and to complete parent-reported questionnaires regarding their perceptions of the Foot Abduction Brace (FAB) and their child's comfort. A minimum of 10 patients per arm will be recruited. A temperature sensor will be added in each participant's boots during the 90-day study period to objectively measure time of brace wear. It is hypothesized that when patients are wearing the DB, they will experience higher brace tolerance defined as increased wear time of the brace as measured by the temperature sensors, and higher comfort levels as reported by parents, without an increase in clubfoot deformity recurrence compared to the SB. Most patient health information will be collected and stored in the SickKids Clubfoot Research Registry (REB #1000053919).
Objectives:	Primary Objective: To evaluate the ease of recruiting and retaining participants for a randomized-controlled effectiveness trial of a novel FAB bar.
	 Secondary Objectives: To compare parental perception of the child's comfort in the SB versus the DB for foot abduction bracing in Ponseti clubfoot treatment. To compare patient tolerance of the SB to the DB by how many hours the brace is worn per day as recorded by temperature sensors placed in the boots and by parent self-reported log of brace wear. To perform a preliminary assessment of the effectiveness of the DB at preventing clubfoot recurrence during the bracing phase when the brace is worn as prescribed for a 30-day trial period.

Endpoints:	Primary Endpoint: Recruitment rate, dropout rate, and related responses
	on the parent-reported survey.
	Secondary Endpoints:
	1) Patient comfort levels determined by parent-reported surveys with 5-
	point Likert scale responses completed at Day 0, Day 30, and Day 90 of the study period
	2) Daily brace wear bours as measured by a parent self-reported log and
	by temperature sensors implanted inside the boots.
	3) Presence of clubfoot recurrence defined as a Pirani score > 0.5
	representing any new development of cavus, adduction and/or
	hindfoot varus, or a loss of passive ankle dorsiflexion (equinus) of < 10
	degrees above neutral or a reduction of 5 or more degrees from the
	previous visit.
Study Population:	20 patients with well-corrected unilateral or bilateral idiopathic clubfoot
	deformity, aged 1 to 3 years, who are using a SB with their FAB for the
	minimum 12-hour per day bracing stage of their Ponseti treatment at the
	Hospital for Sick Children.
Phase:	N/A
Description of Study	There are multiple intervention devices (bars) that will be compared
Intervention:	during foot abduction bracing for clubfoot treatment. The control cohort
	will wear their standard bar with the standard boot for 90 days. The
	experimental cohort will wear a new dynamic bar with the standard boot
	for 30 days, then return to their SB for 60 days. The novel bar is designed
	by the research team and allows independent movement of the knees and
	hips while maintaining a corrective position of the foot.
Study Duration:	5 months
Participant Duration:	3 months

1.2 SCHEMA

1.3 SCHEDULE OF ACTIVITIES (SOA)

Procedures	Screening Day -30 to -1	Baseline, Visit 1 Day 0	Study Visit 2 Day 7+/- 3 days	Study Visit 3 Day 30 +/-7 days	Study Visit 4 Day 90 +/- 7 days
Chart Review for screening	Х				
Measure patients for appropriate size of SB and DB		Х			
Informed consent		Х			
Complete Consent Discussion Form		Х			
Randomization		Х			
Prescribe study intervention (new DB or original SB)		Х			
Launch/retrieve data from temperature sensor in boot		х		х	х
Physical exam		Х	Х	Х	Х
Adverse event review			Х	Х	Х
Administer surveys		Х		Х	Х
Video record patients in their prescribed bar				х	

Procedures	Screening Day -30 to -1	Baseline, Visit 1 Day 0	Study Visit 2 Day 7 +/- 3 days	Study Visit 3 Day 30 +/-7 days	Study Visit 4 Day 90 +/- 7 days
Distribute/collect brace wear log		Х		Х	Х
Document on study enrollment log	Х	Х	Х	Х	Х

2 INTRODUCTION

2.1 BACKGROUND

Clubfoot, also known as congenital talipes equinovarus (CTEV), is the most common congenital orthopaedic deformity, occurring in approximately 1 in 1,000 live births (1). The affected foot is characterized by an excessive down-and-in position (equinovarus) with a high medial longitudinal arch (cavus). Without treatment, clubfoot can result in long-term disability and pain. Standard of care for treatment of clubfoot is the Ponseti method. It consists of gentle manipulation and serial casting of the foot, followed by a percutaneous Achilles tenotomy. The correction is then maintained using a foot abduction brace (FAB). Typical wear schedule for the FAB is 23 hours per day for the first three months, then at night only (aiming for 12 hours per day) until 5 years of age (2). Ideal position for the clubfoot in the FAB is 10 degrees of ankle dorsiflexion and 60 degrees of external rotation with the feet held shoulder-width apart (3).

Foot abduction braces consist of two ankle-foot orthosis (boots) connected by a shoulder-width bar. Most standard bars are straight and significantly limit independent knee and hip movement. Studies have reported that some parents perceived their child is uncomfortable wearing the FABs with a straight bar with up to 61% of idiopathic clubfoot patients not complying to the prescribed bracing schedule (3). Lack of brace tolerance and inadequate time in brace are shown to increase risk of recurrence (3).

Alternative bars for FABs that include hinges for added motion are few. One current and popular design, the Dobbs Bar, has hinges in the coronal plane to provide the patient with some independent mobility of the legs. See Appendix A for images of the Dobbs bar. Studies suggest that this independent mobility is directly correlated to greater comfort, as patients using the Dobbs Bar have greater rates of compliance and lower rates of recurrence (4). However, the Dobbs Bar features a spring-loaded mechanism in the hinge to return the patient's feet to the best-corrected position. Many patients can over-power the springs enabling intermittent loss of the corrective foot position by allowing plantarflexion and inversion of the feet. This might also allow the deforming muscles, the tibialis posterior and the plantarflexors of the feet, to strengthen as they contract against the spring, possibly contributing to further muscle imbalance and increasing the risk of clubfoot recurrence. This bar is also more expensive than the SB and is not covered by the Ontario Assistive Devices Program (5).

2.2 STUDY RATIONALE

This study seeks to evaluate the feasibility of conducting a large-scale clinical trial to evaluate the effectiveness of a newly designed dynamic bar (DB) for foot abduction bracing in clubfoot treatment (see photos in Appendix A). This DB fixes the foot and ankle position relative to two L-shaped brackets at the end of each bar, in order to maintain a corrective foot position at all times during use and prevent over-activation of deforming muscles. It allows independent extension and flexion the knees and hips while restricting motion of the ankle into plantarflexion or inversion as the latter movements may

contribute to muscle imbalance or recurrence of the clubfoot deformity. It is hypothesized that this added leg mobility would reduce brace intolerance and improve child comfort without increased risk of recurrence.

Brace non-compliance is the leading cause of clubfoot recurrence (6,7). Reported recurrence rates after correction range from 20-41% and are higher the earlier the brace is discontinued (6). According to the Ponseti International website, the rate of recurrence when brace wear stops in the first year is 90%, 70–80% in the second year, 30–40% in the third, 10–15% in the fourth, and approximately 6% in subsequent years. (3) Intolerance and non-adherence to bracing affects an average of 35% of patients and can increase recurrence rates by anywhere 5- to 17-fold (3,6,7,8). The large variation in reported brace intolerance and clubfoot recurrence can be attributed to the lack of consensus regarding the definitions of 'clubfoot recurrence' and 'non-compliance' to bracing, as well as variation in the prescribed bracing schedules (7,9).

Brace compliance and actual brace-wear hours are very challenging to assess, and most studies only include parent-reported wear schedules (7). Studies have shown that parents tend to over-report daily brace wear times. To address this, we will use a small temperature sensor placed in each patient's boots. These sensors have been used in past studies to provide objective measurements of daily bracing wearing times by measuring the temperature increase when the child is in the brace (10, 11,12). Automating the recording of daily brace wear will reduce human error and enable the study's endpoints to be assessed more accurately.

Our new DB prototype has been trialed for a 10-minute period on 7 patients in the clubfoot clinic at the Hospital for Sick Children (SickKids) during their already scheduled follow up visit. This informal evaluation was conducted to get a sense of fit and motion and identify any critical aspects that might inform adjustments to the prototype design. Short surveys were administered to the physiotherapist applying the FAB and the parent to learn of their initial impressions of the DB (see Appendix B). Parent feedback was largely positive, and 6 out of 7 parents indicated that they would prefer their child to use a brace that gives them more freedom to move their feet. Physiotherapist assessment also confirmed that the bar maintains proper foot position and leg alignment during use.

2.3 RISK/BENEFIT ASSESSMENT

This DB has the potential to greatly improve patient and parent experience with clubfoot bracing during the night-time phase of treatment. By increasing the patient's independent leg motion and comfort, brace tolerance should improve, and in turn, reduce the risk of relapse. By increasing brace wear, brace comfort and minimizing recurrence, this new bar design should lead to improved clinical outcomes, as well as patient and parent-reported outcomes.

The risks associated with the use of the DB prototypes includes all the risks associated with SBs, such as pressure sores and skin rashes. Additional risks associated with the DB might include bar malfunction or breakage, due to lack of extensive material evaluations. Clubfoot recurrence still occurs with the SB, but the risk may be increased with the DB as it will give patients unprecedented mobility. Walking in any foot abduction brace is not recommended, however the added mobility provided by the DB might enable safer mobility for the child possibly preventing injury and falls. To mitigate risks and complications, a blinded outcomes assessor will regularly evaluate the patients, and if any sign of clubfoot recurrence is observed, the child will immediately return to their original FAB with serial casting

as needed. The intervention period in this feasibility study is purposely short to avoid placing a child in a potentially ineffective brace for a prolonged period of time.

3 OBJECTIVES AND ENDPOINTS

OBJECTIVES	ENDPOINTS	JUSTIFICATION FOR ENDPOINTS	
Primary			
To evaluate the ease of recruiting and retaining	Recruitment rate, dropout rate, and related responses on	This informs on the potential barriers to recruitment and	
participants for a randomized- controlled effectiveness trial of a novel FAB bar.	the parent-reported survey.	scale clinical trial to evaluate the effectiveness of the DB.	
Secondary			
1) To compare parental perception of the child's comfort in the SB versus the DB for foot abduction bracing in Ponseti clubfoot treatment.	1) Patient comfort levels determined by parent- reported surveys with 5-point Likert scale responses completed at Day 0, Day 30, and Day 90 of the study period.	1) Child comfort in brace is critical to achieving full brace compliance. As our study subjects are aged 1-3 years and unable to complete surveys or communicate their experience, parent-proxy reported outcome measures are a validated method to use as an endpoint (13, 14).	
2) To compare patient tolerance of the SB to the DB as measured by parent self-reporting and by how many hours the brace is worn per day as recorded by temperature sensors placed in the boots.	2) Daily brace wear hours as measured by a parent self- reported log and by temperature sensors implanted inside the boots.	2) Brace non-compliance is the leading cause of clubfoot recurrence. Therefore, increasing brace tolerance decreases clubfoot recurrence and leads to improved clinical outcomes.	
3) To perform a preliminary assessment of the effectiveness of the DB at preventing clubfoot recurrence during the bracing phase when the brace is worn as prescribed for a 30-day trial period.	3) Presence of clubfoot recurrence defined as a Pirani score > 0.5 representing any new development of cavus, adduction and/or hindfoot varus, or a loss of passive ankle dorsiflexion (equinus) of < 10 degrees above neutral or a reduction of 5 or more degrees from the previous visit.	3) While there is no validated definition for clubfoot recurrence, our clinical endpoints are commonly used criteria in other clubfoot studies. Since this is a feasibility study with only 20 participants, safety and efficacy cannot be clinically proven but we want to ensure the design at least prevents early relapse during the night-time bracing phase before the DB is produced at-large.	

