4 STUDY DESIGN

4.1 OVERALL DESIGN

This is an assessor-blinded randomized controlled trial in which patients with well-corrected idiopathic clubfoot will be randomized to wear either their original SB (which is standard care for clubfoot treatment) or the new DB for 30 days. After 30 days, all participants will resume use of the SB and be monitored for an additional 60 days.

This study is a "feasibility trial" as it is assessing the feasibility of conducting a large-scale randomized controlled trial to evaluate the effectiveness of the DB. As such, feasibility will be determined by the ability to recruit patients within the goal study period and to retain participants.

On Day 0 of the study period, patients will be randomized and receive baseline clinical and questionnaire evaluations. A temperature sensor will be added in each participant's boots during the 90-day study period to objectively measure time of brace wear.

All patients will be evaluated after 7 days in their assigned bar to check for brace fit, any complications, and to perform required adjustments. This 7-day checkup is standard care for clubfoot treatment when patients receive the SB and FAB for the first time.

After 30 days, the patients wearing the DB will resume use of the SB. All patients will be seen at the end of the first 30 days and after 90 days to monitor for recurrence of the clubfoot deformity, complications of brace wearing, and parent-reported perception of their child's comfort with the FAB. Parents will also be asked to complete a self-reported brace wear log that will be collected on Day 30 and 90.

A minimum of 10 patients per arm will be recruited. Once there are 10 in each arm, recruitment will halt. It is hypothesized that patients using the DB will experience higher brace tolerance as measured by the temperature sensors, and higher comfort levels as reported by parents, without an increase in clubfoot deformity recurrence compared to the SB.

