4.2 SCIENTIFIC RATIONALE FOR STUDY DESIGN

This trial design allows for direct comparison between SBs and the new DB, without affecting the patient's long-term treatment plan or outcomes. The assessments will be between patients (control vs. experimental cohorts) and within the same patient (experimental cohort wearing both bar designs).

Since participants in this feasibility trial will only use the DB for a maximum of 1 month, the likelihood of finding a difference in bar effectiveness is quite low. Therefore, following this feasibility trial, the study team plans to conduct a prospective randomized controlled trial of the novel DB versus standard bars, comparing the DB's effectiveness at maintaining ideal foot position and preventing recurrence over a minimum two-year period. A separate REB application will be filed for this trial.

Bias in brace wear reporting will also be mitigated in this feasibility study by using temperature sensors to objectively measure the time of brace wear, and by using quantitative evaluations done by blinded outcomes assessors to evaluate study endpoints.

To mitigate the risk of bias in the completion of the parent-reported surveys, the surveys were written using neutral language as much as possible. For example, instead of using the terms "standard" and "dynamic," the bar types were described using the terms "current," "original," and "alternative."

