9.2 POPULATIONS FOR ANALYSES

The following study populations are defined and will be analyzed as specified below:

- Intent to treat population: the total population of patients registered in the study.
- Experimental arm population: all registered participants in the experimental arm with DB.
- Control arm population: all registered participants in the control arm with SB.

- Safety population: all registered participants who wore their FAB as prescribed for the full 90-day study period.
- Brace discomfort population: all registered participants who have any history of brace intolerance or indicated in the parent-reported survey that they are not comfortable/have concerns with their original FAB.
- Brace comfort population: all registered participants who have no history of brace intolerance and indicated in the parent-reported survey that they are comfortable/have no concerns with their original FAB.

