9.3.3 ANALYSIS OF THE SECONDARY ENDPOINTS

Parent-reported comfort levels will be determined by parent-reported surveys with 5-point Likert scale responses. Results from these surveys will be analyzed with descriptive statistics for the intent to treat population, the brace discomfort population, and the brace comfort population.

Daily bracing times will be measured by a temperature sensor added in each patient's boots for the entire 90-day study period. The number of hours the brace is worn per day will be divided by the standard number of desirable hours in brace (12 hours) in order to obtain a fraction that quantifies the patient's adherence to the FAB. Mean 'adherence fractions' will be calculated for patients in each arm, and then compared using descriptive statistics. This analysis will be performed for the intent to treat population, the brace discomfort population, and the brace comfort population. This data will be compared to the self-reported brace wear hours by parents in their daily logs.

To ensure minimal efficacy of the DB prototype, all signs of clubfoot recurrence will be carefully examined at each study visit. The null hypothesis is that 'the dynamic bar does not lead to higher rates

of clubfoot recurrence,' and it will be rejected if the number of patients in the safety population that develop clubfoot recurrence during the 90-day study period, is substantially greater in the experimental arm than it is in the control arm (i.e. more than 2 instances of clubfoot recurrence in the experimental arm than in the control arm). Note that this endpoint is not intended to prove safety or efficacy, but rather to ensure that the design may prevent early recurrence before a larger-scale trial is conducted. Clubfoot recurrence is defined as a Pirani score > 0.5, a new occurrence of cavus, adduction and/or hindfoot varus, or a loss of passive ankle dorsiflexion (equinus) of < 10 degrees above neutral or a reduction of 5 or more degrees from the previous visit. Note that all clinical tests required to diagnose recurrence are routinely performed as standard clubfoot care.

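### Objective 3 concerns 30 days of wear on the dynamic bar, but section 9.3.3 plans only a pooled 90-day recurrence count, so recurrence on the bar cannot be told from recurrence after its return

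*Combined protocol and SAP*

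**What the plan says.** Section 3 and the synopsis (1.1) word secondary objective 3 alike: a preliminary look at whether the DB prevents recurrence "when the brace is worn as prescribed for a 30-day trial period". The matching endpoint defines a recurrence but gives no time window.

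The only comparison planned for that endpoint is in section 9.3.3. It uses "the number of patients in the safety population that develop clubfoot recurrence during the 90-day study period" and rejects the null hypothesis if there are "more than 2 instances of clubfoot recurrence in the experimental arm than in the control arm". The safety population in section 9.2 is "all registered participants who wore their FAB as prescribed for the full 90-day study period".

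On exposure, the synopsis has the experimental arm wear the DB "for 30 days, then return to their SB for 60 days". Section 4.1 says: "After 30 days, all participants will resume use of the SB and be monitored for an additional 60 days". Section 4.2 also limits DB use to a maximum of one month.

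On timing of assessment, section 9.3.3 says "all signs of clubfoot recurrence will be carefully examined at each study visit", and the schedule in section 1.3 lists a physical exam at Days 0, 7, 30 and 90. No count at Day 30 is planned, and no split of recurrences at Day 30.

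**The concern.** The objective is about the DB while it is worn. The count covers three times that period, and the DB is out of use for the last two thirds of it. A recurrence first seen at Day 90 in a child who returned the DB sound at Day 30 counts the same as one found at Day 30.

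This matters because section 9.3.3 presents the rule as a check on the design before a larger trial. If the rule triggers, the team will want to know whether the extra recurrences arose on the DB or after the change back to the SB. If it does not trigger, they will want to know how many recurrences arose on the DB at all. The planned result answers neither question.

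**Working it through.** The plan gives no error rate or sensitivity for the rule, so there is no figure of its own to reproduce.

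**Share of the window off the DB.** 60/90 = 67%. With the ±7-day visit windows of section 1.3, the range is (83 − 37)/83 = 55% to (97 − 23)/97 = 76%.

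**Inputs to the rule.** 10 per arm (section 4.1), all assumed to be in the safety population. The rule triggers when experimental minus control is 3 or more (section 9.3.3). The documents give no 30-day or 90-day risk, so I assume a 30-day SB risk *s* of 2%, 5% or 10%. As a guide to scale, section 9.1 assumes 30% control-arm recurrence for the future trial, which section 4.2 says will follow children for at least two years. Spread evenly over 24 months (an assumption), that is 1 − 0.7^(1/24) = 1.5% a month, near the low end of the range.

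**Risks by window.** Let *d* be the assumed 30-day risk on the DB, with the SB risk applying to both arms afterwards.
- SB arm at 90 days: 1 − (1 − s)³. For s = 10%: 1 − 0.9³ = 27.1%.
- DB arm at 90 days: 1 − (1 − d)(1 − s)². For d = 30%: 1 − 0.7 × 0.9² = 43.3%.

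**Where the recurrences fall.** With equal bars, the share of experimental-arm recurrences that first arise after the DB is returned is 1 − s/[1 − (1 − s)³]. This is 66%, 65% and 63% for s = 2%, 5% and 10%.

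**Chance that the rule triggers.** Exact probability from two independent binomials:

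| 30-day risk, SB v DB | Equal bars (both at SB risk), Day 30 | Equal bars, 90 days | DB worse, Day 30 | DB worse, 90 days |
|---|---|---|---|---|
| 2% v 10% | 0.1% | 1.0% | 6.0% | 9.1% |
| 5% v 20% | 0.7% | 5.2% | 23.4% | 25.9% |
| 10% v 30% | 3.0% | 10.2% | 38.3% | 34.1% |

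**Bias or noise.** With equal bars the expected excess is zero in either window. At s = 10% its standard deviation rises from √(20 × 0.10 × 0.90) = 1.34 children at Day 30 to √(20 × 0.271 × 0.729) = 1.99 at Day 90. The threshold stays at more than 2, so false alarms rise.

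**The case against.** The best defence is that "30-day" in the objective describes how long the DB is worn, not how long recurrence is counted. Thirty days of exposure with follow-up to Day 90 in both randomised arms is an ordinary design, and it can catch recurrence that appears after the DB is returned. The table above assumes that all DB harm shows by Day 30. If half the excess in the 10% v 30% case appeared only later, the Day 30 comparison would be 10% v 20% and its sensitivity 16.6%, while the 90-day count would keep 34.1%. The stakes are also limited: this is a secondary, descriptive endpoint in a 20-child feasibility trial, and section 9.3.3 says it is not meant to prove safety or efficacy.

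Most of this stands, and it is a good reason to keep the 90-day comparison. It does not justify having only that comparison. The plan gives no such reason for its window, and a pooled count still cannot show which recurrences arose on the DB.

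A reader might go further and infer that SB-period recurrences are wrongly charged to the DB. The documents do not support that. The rule is a between-arm excess, both arms wear the SB after Day 30, and equal SB-period risk cancels in expectation. A reader might also infer that the longer window makes the rule less sensitive. In two of the three cases above it is slightly more sensitive.

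**Conclusion.** The objective and the planned analysis do not line up. Objective 3 concerns the DB over 30 days of wear. Section 9.3.3 gives one pooled 90-day figure, with 67% of the window on the SB in both arms and no Day 30 result beside it.

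The consistent statistical cost is more false alarms: from 0.1%, 0.7% and 3.0% to 1.0%, 5.2% and 10.2% at assumed 30-day SB risks of 2%, 5% and 10%. At risks near 2% or below the cost is small in absolute terms. Sensitivity goes either way. These figures rest on assumed risks, a constant SB risk after Day 30, DB harm confined to the first 30 days, and 10 evaluable children per arm.

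It would be too strong to call the 90-day count invalid, or to say that the rule should simply move to Day 30. The 90-day count is a fair comparison of the two assigned sequences. What is missing is a separate result for the period on the DB. This is a worthwhile improvement to a secondary analysis, and the primary feasibility endpoint is not affected.

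**What to change.** In section 9.3.3:
- Report the between-arm recurrence comparison up to and including the visit at which the DB is returned (Day 30) as the result that addresses Objective 3.
- Show recurrences first found after that visit and up to Day 90 separately, by arm.
- Keep the total 90-day comparison, stated as the check for delayed recurrence.

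In Objective 3 and section 9.3.3, state which window each conclusion rests on and which one the more-than-2 threshold applies to. If the threshold is applied to both, the chance of at least one false alarm cannot be lower than the 90-day figure. The safety population is also defined by 90 days of wear, so name the analysis set for the Day 30 comparison.

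The cost is wording and one extra table. The Day 7, 30 and 90 exams are already scheduled, and section 8.2.5 already records onset dates of adverse events. The downside is that the Day 30 comparison holds fewer events and misses harm that appears late, which is why the 90-day comparison stays.
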